Moving forward, Project HEAL will continue to communicate with sites/chapters about any number of topics in addition to the Communities of HEALing study. From this point forward, all peer mentorship will take place in the context of the research study (mentorship will not be offered outside of the study). We will communicate with Project HEAL leadership to implement the study. All communication for the purpose of research assessments and data collection will be direct communication between EDRU research staff and study participants. We will provide supervision directly to peer mentors and social support mentors. We communicate directly with participants (and inform Project HEAL) regarding randomization (treatment assignment) and matching.

Project HEAL sites for its mentorship program currently include New York, Philadelphia, Los Angeles, San Francisco, Boston, Chicago, Essex, MA, Southeast Pennsylvania, and Pittsburgh. Interested participants who do not live in the vicinity of an existing Project HEAL site are offered available online peer mentors with whom they may communicate via FaceTime or Skype. Peer mentors provide support, guidance, and share personal experiences in order to help mentees cope with challenges to recovery and navigate day-to-day difficulties related to their eating disorder. Peer mentors and their mentees connect once per week in-person (for those from the areas described above) or online (for those who live outside of commutable distance from the identified sites) for one hour. Peer mentor/mentee interactions are focused on the mentee’s eating disorder recovery process, and includes structured topics/activities like examining pros and cons of behavior change and challenging eating disorder thoughts. Peer mentorship is *not* designed as a standalone intervention and requires participants in the program to be involved in concurrent treatment with a licensed professional.

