Project HEAL’s mentorship program is one of the first programs of its kind. Given the project’s nascence, its acceptability and effectiveness have not been evaluated, and Project HEAL has asked Drs. [name] and [name] and the Columbia Eating Disorders Research Unit (EDRU) to evaluate it by conducting a randomized controlled trial comparing mentorship to two other conditions also carried out by Project HEAL. The two comparison programs are a non-eating disorder-focused social support condition (for six months) and a wait-list control (for six months). In the social support condition, individuals with an eating disorder are matched with a “social support mentor” without a history of an eating disorder. Social support mentors coordinate social activities within Project HEAL and the community, such as participating in advocacy or leisure activities. Participants assigned to this condition engage in an activity per week (lasting approximately one hour) with their social support mentor and in some cases, 1-2 other mentees. Interactions are centered on the week’s activity (e.g., writing a letter to a representative, viewing museum exhibit), with an *intentional focus outside the eating disorder*. Wait-list participants engage in treatment with their outpatient providers for six months (as do patients in both active conditions), and then they are offered a mentor for six additional months. They may choose whether they prefer a peer mentor or a social support mentor. Interventions were developed by Project

HEAL and tailored to suit a research context with input from EDRU investigators. Program descriptions and manuals are provided for context.

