Aim 2: Evaluate the impact of intervention condition on eating disorder symptoms. Hyp 2a. Participants in peer mentorship will have greater reductions in eating disorder symptoms, measured using the Eating Disorder Symptom Inventory (EPSI), compared to both control conditions. Hyp2b: For individuals who meet criteria for current or past anorexia nervosa, individuals assigned to peer mentorship will be more likely to achieve or maintain a BMI ≥ 18.5 , compared to both control conditions. Hyp2c: For individuals who meet criteria for current or past bulimia nervosa or binge eating disorder, individuals assigned to peer mentorship will be more likely to abstain from bingeing/purging and bingeing episodes, respectively, compared to individuals in either control condition.

Aim 3: Evaluate the impact of intervention condition on total cost for eating disorder treatment. Hyp 3. Estimated total cost for eating disorder treatment, measured using the Healthcare Utilization Survey, will be lower among peer mentorship participants compared to both control groups at (i) post-treatment and (ii) one-year follow up.

Exploratory Aim: Evaluate characteristics of individuals participating as peer and social support mentors. Exploratory hypothesis: Mentor characteristics and similarity between mentee and mentor characteristics will not influence mentee outcomes (acceptability, eating disorder symptoms, and estimated treatment cost).

Inclusion/Exclusion Criteria

This section details your study sample(s) and addresses the requirement for risk minimization. You may choose to divide your sample by population (healthy controls vs. subjects) or by procedure (subjects who will have an MRI) and then define different sets of criteria for each.

For each sample, create or insert a table to describe detailed criteria for study inclusion and exclusion and the method you will use to ascertain each criterion. The method of ascertainment may describe tests, scales and instruments. When relevant, indicate the level of training of the person who will make the assessment (e.g. clinical interview by a psychiatrist).

Inclusion/Exclusion Criteria needs to be numbered and listed in outline form (see Table template below)

Mentees (Adolescents or adults with anorexia nervosa, bulimia nervosa, or binge eating disorder):

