To promote retention, participants will be contacted at two and five months by Project HEAL staff members, who will remind the participant of the study timeline, indicate when the next assessment will be completed, and remind the participant that he/she will be assigned to an active intervention after the 6-month study period.

Addressing mentee/mentor mismatch: There is a 3-step procedure for addressing instances in which a mentee reports a mismatch with his/her mentor. First, the mentor would receive supervision and make attempts to resolve the mismatch. Second, if the mismatch persists, we will match the mentee with a new mentor one time only. If a mentee has a mismatch with their second mentor, they will not be eligible to be re matched and their participation in the study interventions (mentorship) will be discontinued. If the mismatch occurs because the mentee is not abiding by guidelines for participation and this causes the mentor to feel uncomfortable, the PI/Co-I will speak with the mentee to address the issue. If this persists, the mentee's participation in the mentorship component of the study will be discontinued. Mentee guidelines are attached.

Operationalized criteria for early discontinuation of the active intervention: Grounds for discontinuing the active interventions (meaning that the participant is no longer able to meet with his/her mentor) include the following:

- (a) Not complying or attending outpatient treatment (defined as mentee or provider indicating that the mentee is not attending treatment for 2 weeks or more) *or* not hearing from the mentee's treatment provider for 2 consecutive months.
- (b) Requiring a higher level of care (per the mentee's treatment provider) and choosing not to pursue it.
- (c) Missing 3 consecutive sessions with mentor and/or missing >2sessions/month for 2 consecutive months (without calling ahead to reschedule).
- (d) Requesting >1 mentor reassignment. If the mentee has a mismatch with >1 mentor, we will not be able to assign a third mentor.

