If a mentee is recommended for, and enters, treatment at a higher level of care, he/she may not receive mentorship while receiving treatment at the higher level of care. After discharge, pt may attend any remaining mentorship sessions falling within the study period (months 1 – 6) after providing a new provider clearance form. If the mentee was assigned to the wait list and enters treatment at a higher level of care during months 6 – 12, the same procedure will be followed. We will ask study participants to continue completing questionnaires even if a participant is no longer meeting with his/her mentor (regardless of the reason). Patients may choose whether they wish to continue completing study assessments.

Common intervention components

Recovery Record: Participants in the peer mentorship arm of the study will be asked to utilize Recovery Record®, a HIPPA-compliant smart phone and/or computer application, as a recovery tool only. No data will be collected using this application. The application was designed to provide support to eating disorder patients and includes a number of features aimed to promote recovery, such as a meal tracking record, prompts for completing meals/snacks, tracking for additional symptoms such as stress and mood, motivational messages, information about coping strategies, and capacity to share logged data with clinicians and mentors. Participants in the social support and wait-list control interventions will be informed that Recovery Record® has a number of additional features that they are welcome to explore on their own or in collaboration with their outpatient treatment team. Using the app will not be required if a participant prefers not to use it.

Community support groups: All participants in the study are invited to attend Communities of HEALing support groups, which are offered by Project HEAL but they are not part of the proposed study. Groups may include members of the community who are not involved in research. Participants will be informed at the onset of groups that there are members in the group who are not participating in the research study and it will be up to their discretion whether they choose to attend.

Mentor Training:

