Aim 2: Evaluate the impact of intervention condition on eating disorder symptoms. Hyp 2a. Participants in peer mentorship will have greater reductions in eating disorder symptoms, measured using the Eating Disorder Symptom Inventory (EPSI), compared to both control conditions. Hyp2b: For individuals who meet criteria for current or past anorexia nervosa, individuals assigned to peer mentorship will be more likely to achieve or maintain a BMI ≥ 18.5 , compared to both control conditions. Hyp2c: For individuals who meet criteria for current or past bulimia nervosa or binge eating disorder, individuals assigned to peer mentorship will be more likely to abstain from bingeing/purging and bingeing episodes, respectively, compared to individuals in either control condition.

Aim 3: Evaluate the impact of intervention condition on total cost for eating disorder treatment. Hyp 3. Estimated total cost for eating disorder treatment, measured using the Healthcare Utilization Survey, will be lower among peer mentorship participants compared to both control groups at (i) post-treatment and (ii) one-year follow up.

Inclusion/Exclusion Criteria

This section details your study sample(s) and addresses the requirement for risk minimization.

You may choose to divide your sample by population (healthy controls vs. subjects) or by procedure (subjects who will have an MRI) and then define different sets of criteria for each.

For each sample, create or insert a table to describe detailed criteria for study inclusion and exclusion and the method you will use to ascertain each criterion. The method of ascertainment may describe tests, scales and instruments. When relevant, indicate the level of training of the person who will make the assessment (e.g. clinical interview by a psychiatrist).

Inclusion/Exclusion Criteria needs to be numbered and listed in outline form (see Table template below)

Mentees (Adolescents or adults with anorexia nervosa, bulimia nervosa, or binge eating disorder):

**Note that all EDRU screens will be reviewed with a clinician (MD or PhD level) and if any criteria are in question, the clinician will speak directly with the potential participant by telephone.*

CRITERION	METHOD OF ASCERTAINMENT
Inclusion:	
1. Ages 14 – 45 years	Initial telephone interview with Project HEAL staff, confirmation during telephone screening with EDRU research team member (RA level or higher)*

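### At one year the wait list has already been offered mentors, so Hyp 3(ii) compares immediate with delayed mentorship, and neither Hyp 3 nor the SAP says so

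*Protocol*

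**What the plan says.** Hyp 3 stands under the primary aims in the Protocol's Specific Aims and Hypotheses, and is repeated in the second copy of the form. It predicts that total eating disorder treatment cost "will be lower among peer mentorship participants compared to both control groups at (i) post-treatment and (ii) one-year follow up".

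Background, Significance, and Rationale sets the wait-list period at six months of outpatient care, "and then they are offered a mentor for six additional months". On the type of mentor it adds: "They may choose whether they prefer a peer mentor or a social support mentor". The Wait-list control paragraph has staff remind participants that "he/she will be assigned to an active intervention after the 6-month study period". Matching depends on a provider form at month 6 (Additional procedures to optimize participant safety).

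For the active arms, mentoring is tied to the six-month randomised period. After a return from a higher level of care, "pt may attend any remaining mentorship sessions falling within the study period", given there as months 1 to 6. The safety procedures limit resumed meetings in the same way. Background also says that "mentorship will not be offered outside of the study".

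The Assessments paragraph has all arms assessed monthly to month 6 and again at month 12. The wait list alone is also assessed monthly during its open-label phase.

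The SAP is one paragraph: intent-to-treat; linear mixed models for each outcome with time, group and their interaction; a random intercept; peer mentorship as the reference group. It gives no time range, no coding of time, no named contrast, and no rule for wait-list data after month 6.

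**The concern.** Hyp 3(ii) calls the wait list a control at a time when it is the only arm with a documented offer of mentors. A reader would take the one-year result as peer mentorship against none. A small or non-significant difference could then be reported as no lasting saving, although part of the difference may have been removed by the wait list's own mentoring.

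The second issue is how time enters the model. Without a window or a coding, the symptom analysis (Hyp 2a, which names no one-year test) could be a straight line through month 12. Its slope contrast would then not estimate the six-month effect. The choice could also be made after the data are seen.

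**Working it through.** The documents give no effect size, SD, power or allocation ratio for any outcome, so there is no planned figure to reproduce. What follows is an illustration under stated assumptions.

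**Inputs from the documents.** Wait-list control period 6 months, then 6 months of mentoring offered; active-arm mentoring in months 1-6; 80 completers (Description of Subject Population).

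**Assumptions.** The peer arm's monthly saving rises by 1 unit per month to 6 at month 6, then moves linearly to 6p at month 12 (p = 1 fully kept, p = 0 fully lost). The wait list's monthly saving is k(t - 6) after month 6, where k is uptake times relative benefit.

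1. Cumulative cost, months 0-12. Peer saving: 6 x 6/2 = 18 to month 6, plus 6 x (6 + 6p)/2 = 18 + 18p after it, total 36 + 18p. Wait-list saving: k x 6 x 6/2 = 18k. Contrast: 36 + 18p - 18k. Share removed: 18k/(36 + 18p).

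2. Cumulative cost, months 6-12 only. Contrast: 18(1 + p - k). Share removed: k/(1 + p).

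3. Monthly cost at month 12. Contrast: 6p - 6k = 6(p - k). This is zero at k = p and negative when k exceeds p. For example, p = 0 and k = 0.5 gives -3.

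| k | Share removed, months 0-12 (p = 1 to 0) | Share removed, months 6-12 (p = 1 to 0) |
|---|---|---|
| 0.25 | 8-13% | 13-25% |
| 0.5 | 17-25% | 25-50% |
| 1 | 33-50% | 50-100% |

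4. Power for the 12-month total. With equal allocation assumed, 80/3 is about 27 per arm. A two-sided 5% t-test then has 80% power for 0.78 SD. Removing 17-25% (k = 0.5) leaves 65-56% power. Removing 33-50% (k = 1) leaves 46-29%. The n per arm needed to restore 80% rises by 1/(1 - share)²: 1.4-1.8 times and 2.3-4.0 times. The 80% starting point is itself an assumption.

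5. Symptom slopes with linear time through month 12. The same curves are used for symptom benefit, with the peer arm observed at months 0-6 and 12, the wait list monthly to 12, and a random intercept (intraclass correlations 0.3, 0.5 and 0.7 give identical results). Over months 0-6 the slope contrast is 1.00. Over months 0-12 with p = 1 it is 0.52 at k = 0, 0.27 at k = 0.5 and 0.02 at k = 1. If the peer effect fades it can turn negative: -0.22 at p = 0.5, k = 1, and -0.21 at p = 0, k = 0.5.

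6. Source of the slope loss. The fall from 1.00 to 0.52 occurs with no wait-list benefit at all, because a straight line is fitted over a plateau. Restricting the wait list to the peer arm's visits moves 0.272 only to 0.283 at k = 0.5, and 0.022 to 0.044 at k = 1. The cause is linear time through month 12. The extra wait-list visits contribute almost nothing.

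**The case against.** Hyp 3 itself lists post-treatment and one year separately, and the Assessments paragraph marks the wait list's later phase as open label, so the protocol does draw the boundary. That stands, and it protects the month-6 cost contrast. But no analysis text uses the boundary, and Hyp 3(ii) still calls the wait list a control after it.

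A reader might infer that the one-year contrast is invalid. It is not: participants are analysed as randomised, and the comparison of assigned strategies is sound. What is missing is a statement of which strategies are being compared.

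A reader might also infer that dilution is certain. The documents do not support that. Mentoring depends on staying in outpatient treatment, Background says adjunct support may promote treatment engagement, and the cost survey counts outpatient visits and therapy. Mentoring could therefore raise wait-list cost in months 7-12 and widen the contrast. Nor is every wait-list participant matched, because a month-6 provider form is required.

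It would equally be wrong to say that the contrast cannot reverse. It stays at or above zero for the two cumulative windows under the assumed shape with k at most 1. A monthly cost near month 12 reverses when k exceeds p, and the documents do not give the period that the one-year cost covers.

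Finally, the time-coding gap is general and would exist without wait-list mentoring. That is correct, and it is why it is kept as a separate part of this point.

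**Conclusion.** The point holds and should be fixed. As written, Hyp 3(ii) treats as a control an arm that has been offered mentors since month 6. The one-year wait-list contrast answers a valid question, immediate peer mentorship versus delayed mentorship, but not whether peer mentorship saves cost relative to none.

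If mentoring lowers cost, the illustrative loss is 17-25% of a 12-month cumulative saving at k = 0.5 and 33-50% at k = 1. Direction and size depend on the cost window, on how long the peer effect lasts, and on whether mentoring lowers or raises treatment use. None of these is given, so confidence in the mislabelling is high and confidence in the direction is only moderate.

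Hyp 3(i) at month 6 and peer versus social support at either time point are not affected by wait-list mentoring. With categorical time, the month-6 symptom contrast is not affected either.

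**What to change.** In the SAP:

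- Treat time as categorical, at the visits common to all arms (baseline, months 1-6, month 12) or, for cost, at the visits where cost is collected.
- Name the month-6 contrast as the test of peer mentorship against the wait list as an unmentored control.
- Report the month-12 wait-list contrast from the same model as secondary, labelled immediate peer mentorship versus delayed mentorship.
- Describe wait-list open-label visits between months 6 and 12 separately.
- State the period that the one-year cost covers.

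In the Protocol:

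- Reword Hyp 3(ii) so that the one-year test is peer mentorship versus social support.
- Confirm that the cost survey is given at month 12. Background schedules cost before, midway through and after treatment, and the month-12 list under Assessments does not name it.
- Reconcile what the wait list receives. The lay summary in the submission form says peer mentorship. The lay summary of the protocol summary form says either type. Background gives a choice, and the Wait-list control paragraph speaks of assignment to an active intervention.

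The cost is a few SAP sentences and a reworded hypothesis, plus one survey per participant if cost is not already collected at month 12. The trial gives up a one-year claim against an unmentored control, which the design cannot support. Durability would be shown only relative to social support.
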